8.2.3.1. Safety Review of 12-lead Electrocardiograms

All recorded ECGs will be reviewed by the Investigator or qualified designee. If a participant shows a clinically significant abnormal ECG, additional safety recordings may be made, and the abnormality will be followed to resolution.

8.2.4. Clinical Safety Laboratory Assessments

All protocol-required assessments, as defined in Section 10.2, must be conducted in accordance with the SoA (Section 1.3) and the Laboratory Manual. Clinical and laboratory assessments to assess safety will be performed by a central laboratory.

• The Investigator must review the laboratory report, document this review, and record any clinically relevant changes occurring during the study in the AE section of the eCRF. The laboratory reports must be filed with the source documents. Clinically

Page 51 of 97	
Alexion Confidential	

significant abnormal laboratory findings are those which are not associated with the underlying disease, unless judged by the Investigator to be more severe than expected for the participant's condition.

- All laboratory tests with values considered clinically significantly abnormal during participation in the study will be repeated until the values return to normal or baseline or are no longer considered clinically significant by the Investigator or Medical Monitor.
 - If such values do not return to normal/baseline within a period of time judged reasonable by the Investigator, the etiology should be identified, and Alexion notified.
 - If laboratory values from non-protocol-specified laboratory assessments performed at the institution's local laboratory require a change in participant management or are considered clinically significant by the Investigator (eg, SAE or AE or dose modification), then the results must be recorded in the eCRF.

The maximum total blood volume collected from participants in the study will not exceed 500 mL in 16 weeks. The American Red Cross at the time of completion of this protocol (https://www.redcrossblood.org/faq.html) states that people can give up to 470 mL every 56 days. Therefore, the 500 mL per 16 weeks permitted in this study is approximately consistent with current clinical practice.

8.2.5. Drug and Alcohol Screen

A urine sample for drug screen will be analyzed for the substances listed in Section 10.2. Timing for urine drug screen and alcohol tests is specified in the SoA (Section 1.3).

8.2.6. Pregnancy

Pregnancy data from female participants and female spouses/partners of male participants will be collected from the first dose of ALXN1850 and at the time points specified in the SoA (Section 1.3). Any female participant who becomes pregnant during the study should be considered for discontinuation from the study intervention. If a pregnancy is reported, the Investigator must immediately inform Alexion within 24 hours of awareness of the pregnancy and follow the procedures outlined in Section 10.4.3.

8.2.7. Injection or Infusion Site Evaluation

Subcutaneous injection- or IV infusion-site evaluations will be performed at the time points specified in the SoA (Section 1.3).

8.2.8. Ophthalmological Examination

Ophthalmological examinations will be performed at the timepoints indicated in Section 1.3. The examination will assess for papilledema and signs of ectopic calcification and will include slit-lamp examination and fundoscopy. The ophthalmology examination should be performed by a qualified ophthalmologist or an optometrist (ie, Doctor of Optometry) as long as the optometrist works under the supervision of an ophthalmologist.

Page 52 of 97	
Alexion Confidential	

8.2.9. Renal Ultrasound

A renal ultrasound will be performed at the timepoints indicated in Section 1.3 to assess for the presence of nephrocalcinosis.

8.3. Adverse Events and Serious Adverse Events

The definitions of AEs and SAEs can be found in Section 10.3. All AEs will be reported to the Investigator or qualified designee by the participant.

The Investigator and any qualified designees are responsible for detecting, documenting, and recording events that meet the definition of an AE or SAE and remain responsible for following up AEs that are serious, considered related to the study intervention or study procedures, or that caused the participant to discontinue the study drug (see Section 7).

Procedures for recording, evaluating, follow-up, and reporting AEs and SAEs are outlined in Section 10.3.

8.3.1. Time Period and Frequency for Collecting AE and SAE

All AEs and SAEs will be collected from the signing of the ICF until the final follow-up-visit (See Section 1.3).

Medical occurrences that begin before the start of study drug but after obtaining informed consent will be considered as pretreatment AEs.

All SAEs will be recorded and reported to Alexion immediately and under no circumstance should this exceed 24 hours, as indicated in Section 10.3. The Investigator will submit any updated SAE data to Alexion within 24 hours of awareness.

Investigators are not obligated to actively seek AE or SAE data after conclusion of the study participation. However, if the Investigator learns of any SAE, including a death, at any time after a participant has been discharged from the study, and he/she considers the event to be reasonably related to the study intervention or study participation, the Investigator must promptly notify Alexion.

8.3.2. Method of Detecting AEs and SAEs

The method of recording, evaluating, and assessing causality of AE and SAE and the procedures for completing and transmitting SAE reports are provided in Section 10.3.

Care will be taken not to introduce bias when detecting AEs and/or SAEs. Open-ended and nonleading verbal questioning of the participant is the preferred method to inquire about AE occurrences.

8.3.3. Follow-up of AEs and SAEs

After the initial AE/SAE report, the Investigator is required to proactively follow-up- on each participant at subsequent visits/contacts. All SAEs will be followed up until resolution, stabilization, the event is otherwise explained, or the participant is lost to follow-up (as defined in Section 7.3). Further information on follow-up procedures is provided in Section 10.3.

Page 53 of 97
Alexion Confidential

8.3.4. Regulatory Reporting Requirements for SAEs

- Prompt notification of an SAE by the Investigator to Alexion is essential so that legal obligations and ethical responsibilities toward the safety of participants and the safety of a study intervention under clinical investigation are met.
- Alexion has a legal responsibility to notify both the local regulatory authority and other regulatory agencies about the safety of a study intervention under clinical investigation. Alexion will comply with country-specific regulatory requirements relating to safety reporting to the regulatory authority, Institutional Review Boards (IRBs)/Independent Ethics Committees (IECs), and Investigators.
- Alexion is required to submit individual suspected unexpected serious adverse reaction (SUSAR) reports (defined in Section 10.3.3) in the format of MedWatch 3500 or Council for International Organizations of Medical Sciences (CIOMS) I Form to health authorities and Investigators as required.
- An Investigator who receives an Investigator safety report describing an SAE or other specific safety information (eg, summary or listing of SAEs) from Alexion will review and then file it along with the IB and will notify the IRB/IEC, if appropriate according to local requirements.

8.3.5. Disease-Related Events and/or Disease-Related Outcomes Not Qualifying as AEs or SAEs

Any increase on frequency and/or intensity in the signs/symptoms of the disease under study will be reported as AEs.

8.3.6. Adverse Events of Special Interest

8.3.6.1. Injection Site Reactions

Injection site reactions (ISRs) are defined as AEs localized to the site of study drug administration that occur at any time during study participation that are assessed by the Investigator as possibly, probably, or definitely related to study drug. AE intensity reporting procedures are outlined in Section 10.3.4.

Injection site reactions may occur at any timepoint after study drug administration. There is no additional laboratory testing required for ISRs.

The Investigator is responsible for monitoring for ISRs in patients throughout the duration of the study. As part of the study-required physical examinations, Investigators should evaluate injection sites for signs of reaction(s).

8.3.6.2. Injection-associated Reactions

Injection-associated reactions are defined as systemic AEs (eg, fever, chills, flushing, alterations in heart rate and blood pressure, dyspnea, nausea, vomiting, diarrhea, and generalized skin rashes) occurring during or within 24 hours of the start of SC injection that are assessed by the Investigator to be related to the study drug. AE intensity reporting procedures are outlined in Section 10.3.4.

Page 54 of 97
Alexion Confidential

8.4. Treatment of Overdose

For this study, any dose of ALXN1850 greater than that specified in this protocol will be considered an overdose.

Overdoses are medication errors that are not considered AEs unless there is an untoward medical occurrence resulting from the overdose. There is no specific treatment for an overdose.

In the event of an overdose, the Investigator should:

- 1. Contact the Medical Monitor immediately.
- 2. Closely monitor the participant for any AE/SAE.
- 3. Obtain a plasma sample for PK analysis if requested by the Medical Monitor (determined on a case-by-case basis).
- 4. Document the quantity of the excess dose as well as the duration of the overdose in the eCRF.

8.5. Pharmacokinetics

- Whole blood samples will be collected for measurement of plasma concentrations of ALXN1850 as specified in the SoAs (see Section 1.3). Additional samples may be collected during the study if warranted and agreed upon between the Investigator and Alexion.
- Instructions for the collection and handling of biological samples will be provided by Alexion. The actual date and time (24-hour clock time) of each sample will be recorded. Permitted collection windows are specified in the SoAs (see Section 1.3).
- Samples will be used to evaluate the PK of ALXN1850. Samples collected for analyses of ALXN1850 plasma concentration may also be used to evaluate safety or efficacy aspects related to concerns arising during or after the study. Unused samples may be retained for a period of up to 5 years (or per regional requirements) to perform additional PK assessments as necessary.
- Samples may be used for research to develop methods, assays, for prognosis, diagnostics, and/or treatment monitoring related to the mechanism of action of ALXN1850.

8.6. Pharmacodynamics

- Whole blood samples will be collected for measurement of PLP/PL, PA, and PPi as specified in the SoA (see Section 1.3). Additional samples may be collected during the study if warranted and agreed upon between the Investigator and Alexion.
- Instructions for the collection and handling of biological samples will be provided by Alexion. The actual date and time (24-hour clock time) of each sample will be recorded. Permitted collection windows are specified in the SoAs (see Section 1.3).
- Samples will be used to evaluate the PD of ALXN1850. Samples collected for analyses of ALXN1850 concentration may also be used to evaluate safety or efficacy

Page 55 of 97	
Alexion Confidential	

aspects related to concerns arising during or after the study. Unused samples may be retained for a period of up to 5 years (or per regional requirements) to perform additional PD assessments as necessary.

• Samples may be used for research to develop methods, assays, for prognosis, diagnostics, and/or treatment monitoring related to the mechanism of action of ALXN1850.

8.7. Genetics

To confirm eligibility, genetic testing for *ALPL* gene mutation will be performed during the Screening Period. No additional samples will be obtained for other genetic analysis during this study.

8.8. Biomarkers

Hypophosphatasia is characterized by interdependent clinical manifestations, emanating from a failure to mineralize bone matrix due to elevated concentrations of the TNSALP substrates, including PPi and PLP. Failure to mineralize bone matrix results in osteomalacia (softening of bones). Bone turnover markers such as osteocalcin, N-terminal propeptide of type I procollagen (P1NP), and serum C-telopeptide cross-link of type 1 collagen (sCTX) are a series of protein or protein derivative biomarkers released during bone remodeling due to activity of osteoblasts or osteoclasts. Bone turnover markers respond rapidly to changes in bone physiology; therefore, they have utility in determining patient response to and compliance with therapies for bone metabolic disorders (Greenblatt, 2017).

Blood samples for bone turnover marker analysis (osteocalcin, P1NP, and sCTX) will be collected at the time points indicated in Section 1.3.

Unused samples may be retained for a period of up to 5 years (or per regional requirements) to perform additional assessments as necessary.

Samples may be used for research to develop methods, assays, for prognosis, diagnostics, and/or treatment monitoring related to the mechanism of action of ALXN1850.

8.9. Immunogenicity Assessments

Antibodies to ALXN1850 (ie, ADA) will be evaluated in serum samples collected from all participants according to the SoA (see Section 1.3). Additionally, serum samples should also be collected at the final visit from participants who discontinued the study intervention or were withdrawn from the study. These samples will be tested by Alexion or Alexion's designee.

Serum samples will be screened for antibodies binding to ALXN1850 and the titer of confirmed positive samples will be reported. Other analyses may be performed to further characterize the immunogenicity of ALXN1850.

The detection and characterization of antibodies to ALXN1850 will be performed using a validated assay method by or under the supervision of Alexion. Samples collected at the same time points as those collected for detection of ALXN1850 antibodies will be evaluated for ALXN1850 concentration to enable interpretation of the antibody data. Antibodies may be further characterized and/or evaluated for their ability to neutralize the activity of the study drug.

Page 56 of 97	
Alexion Confidential	

Samples will be analyzed on a per batch basis. In the event that a participant experiences an SAE potentially related to immunogenicity, that participant's sample or set of samples will be sent for analysis at the time of the event and data will be provided to the SRC. Unused samples may be retained for a period of up to 5 years (or per regional requirements) to perform additional assessments as necessary.

Samples may be used for research to develop methods, assays, for prognosis, diagnostics, and/or treatment monitoring related to the mechanism of action of ALXN1850.

Participants who are positive for ADAs at the last assessment of the study will be given options to enable further monitoring of their ADA values after the end of the study; these options may include enrollment in the Global HPP Registry.

Antibodies to asfotase alfa will also be evaluated in participants who have previously received asfotase alfa at Screening.

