2.3.3. Overall Benefit Risk Conclusion

This is the first time that ALXN1850 will be administered to humans. Because of the potential for immunogenicity, this study will enroll adults with HPP who are not anticipated to require continued treatment with ERT, based on their signs and symptoms, and the Investigator's clinical assessment of their current condition.

Page 33 of 97
Alexion Confidential

This study has been designed to minimize the identified potential risks to participants; there are strict inclusion/exclusion criteria with a robust safety monitoring and risk mitigation plan in place. A SRC will evaluate the available study data at prespecified time points for participant safety and make recommendations on dose escalation, dose modification, or termination of the study. There is no added medical benefit for the participants.

Page 34 of 97	
Alexion Confidential	

OBJECTIVES AND ENDPOINTS 3.

The study objectives and corresponding endpoints are presented in Table 4.

Table 4: **Objectives and Endpoints**

Objective	Endpoints
Primary	
Assess the safety and tolerability of ALXN1850 given IV as a single dose and given SC in 3 qw doses	Incidence of TEAEs and TESAEs
Secondary	
Assess the PK of single IV and 3 SC doses of ALXN1850	ALXN1850 PK (activity) over time profiles and PK parameters
Assess the absolute bioavailability of ALXN1850 SC	AUC _{tau} values of the first SC versus IV administration
Assess the PD effects of single IV and 3 SC doses of ALXN1850	Absolute change and percent change from baseline in plasma concentrations of PPi and PLP and PLP/PL ratio over time
Assess the immunogenicity potential of ALXN1850	Incidence of ADAs and NAbs
Exploratory	
Explore role of ALXN1850 on calcium and bone homeostasis and other PD biomarkers	Absolute, change, and percent change from baseline in ionized Ca, phosphorus, magnesium, PTH, CTX-1 (sCTX), P1NP, osteocalcin, and PA over time
Abbreviations: ADA = antidrug antibody; AUC _{tau} = area u	inder the plasma concentration versus time curve within
the dosing interval; Ca = calcium; IV = intravenous; NA of type I procollagen; PA = pyridoxic acid; PD = pharm	

PL = pyridoxal; PLP = pyridoxal-5'-phosphate; PPi = inorganic pyrophosphate; PTH = parathyroid hormone; qw = weekly; SC = subcutaneous; CTX-1 (sCTX) = serum Ctelopeptide cross-link of type 1 collagen;

TEAE = treatment emergent adverse event; TESAE = treatment emergent serious adverse event

Page 35 of 97	
Alexion Confidential	

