4.4. Analysis Sets

The following analysis sets will be used in the statistical analyses:

- Safety Set: The Safety Set will include all participants who receive any amount of study drug. Participants will be analyzed according to the study drug received.
- Pharmacokinetic Set: The PK Set will include all treated participants for whom the PK profile of ALXN1850 can be adequately characterized. Pharmacokinetic analyses will be based upon the study drug received.
- Pharmacodynamic Set: The PD Set will include all treated participants for whom the PD profile of ALXN1850 can be adequately characterized.
- Immunogenicity Analysis Set: The Immunogenicity Analysis Set will include all treated participants who received any study drug and who after the first dose have at least one reportable result in the ADA assay. Anti-drug antibody analysis will be conducted based on the actual treatment they receive.

5. Participant Disposition

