Individual plasma concentrations of ALXN1850 for each treatment will be presented in data listings and summarized separately using descriptive statistics (N, n [non-missing values within the population], arithmetic mean, SD, %CV, median, minimum, and maximum) by cohort, study day, and scheduled time point. All participants (first and subsequent) will be summarized together for Days 1-8 (predose) for each cohort, after Day 8 only subsequent participants data will be summarized and whereas first participant data will be presented separately. An additional sensitivity analysis will be performed by combining subsequent participants with the first participant (following each SC dosing, ie, SC Dose 1, SC Dose 2, and SC Dose 3) whe re data (corrected from prior carryover exposure post IV dose) is summarized by cohort and scheduled timepoints relative to each dose.

Individual plasma concentrations for ALXN1850 will be plotted for each participant by actual time on both linear and semi-logarithmic scales. Mean plasma concentrations of ALXN1850 versus nominal time will be plotted for each treatment on both linear and semi-logarithmic scales. In addition, mean plasma concentrations of ALXN1850 versus nominal time will be plotted for each treatment by ADA status on both linear and semi-logarithmic scales. The definition of ADA status (ADA negative and ADA positive, and/or pre-existing immunogenicity, treatment-emergent ADA responses, and treatment-boosted ADA responses if data permits, the definition for the ADA response categories is described in the Section 11 of Immunogenicity Analysis).

Individual and mean plasma trough concentrations (C_{trough}) for ALXN1850 versus day following subcutaneous dose administration will be plotted on both linear and semi-logarithmic scales. Time to reach steady state will be graphically assessed by plotting mean plasma C_{trough} concentration versus study day in both linear and semilogarithmic scales.

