Absolute, change, and percent change from the baseline in mean plasma PLP, PLP/PL ratio, and PPi concentration versus time data will be presented graphically by cohort and by ADA status (ADA negative and ADA positive, and/or pre-existing immunogenicity, treatment-emergent ADA responses, and treatment-boosted ADA responses if data permits) over timepoints relative to dose for all participants. This mean figure will be repeated including all participants up to 1 week post IV dose and subsequent participants for the remaining relative time to dose. In addition, the value of plasma PLP, PLP/PL ratio, and PPi for each participant will be presented graphically overlaid with ADA status over timepoints relative to dose.

All data for PPi, PLP, and PL will be presented in data listings.

11. Immunogenicity Analysis

All immunogenicity analyses will be performed on the Immunogenicity Analysis Set.

Asfotase alfa ADA and NAb will only be tested in participants who have previously received asfotase alfa. Immunogenicity analyses (ALXN1850 ADA and NAb) will be performed on samples collected at timepoint shown below:

First participant within each cohort	Subsequent participants within each cohort
Day 1 (pre IV dose)	Day 1 (pre IV dose)
Day 8 (1 week post IV dose)	
Day 15 (pre SC dose 1)	Day 8 (pre SC dose 1)
Day 22 (pre SC dose 2)	Day 15 (pre SC dose 2)
Day 29 (pre SC dose 3)	Day 22 (pre SC dose 3)

Page 25 of 29

First participant within each cohort	Subsequent participants within each cohort
Day 36 (1 week post SC dose 3)	Day 29 (1 week post SC dose 3)
Day 51 (3 weeks post SC dose 3)	Day 43 (3 weeks post SC dose 3)
Day 65 (5 weeks post SC dose 3)	Day 57 (5 weeks post SC dose 3)
Day 85/ED/EoS (8 weeks post SC dose 3)	Day 78/ED/EoS (8 weeks post SC dose 3)

Immunogenicity testing (asfotase alfa ADA and NAb) will be performed at Screening for participants who have previously received asfotase alfa.

Anti-drug antibody variables include ADA response category incidence and titer over the duration of the study will be defined as:

- ADA negative: ADA negative response in the ADA assay at all time points.
- ADA positive: include participant with a positive response in the ADA assay at any time point will be categorized as follows:

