 - O Pre-existing immunogenicity: Defined as ADA positive result in the assay at baseline with all post first dose ADA results negative or a positive result at baseline with all post first dose ADA results less than 4 folds over the baseline titer levels.
 - Treatment-emergent ADA responses: Defined as a positive result in the ADA assay post first dose, when baseline results are negative or missing.
 - Treatment-boosted ADA responses: Defined as a positive result in the ADA assay post first dose, that is greater than or equal to 4-fold over baseline titer levels, when baseline results are positive.

NAb response category will be defined as below

- NAb positives: a positive result in the NAb assay post first dose, in a participant with treatment-emergent or treatment-boosted ADA responses.
- Or will be NAb negative.

The incidence of ADA response categories (negative, pre-existing immunogenicity, treatment-emergent ADA responses, and treatment-boosted ADA response) will be summarized as absolute occurrence (n) and percentage (%) by cohort. The summary statistics of maximum ADA titer levels will be summarized for ADA positive participants by cohort. Listing of maximum ADA titer level for ADA positive participants will be provided.

NAb positive and NAb negative will be summarized as absolute occurrence (n) and percentage (%) by cohort. Listing for NAb positive participants will be provided for treatment-emergent and treatment boosted participants.

The ADA titer will be summarized by cohort and relative to each dose. The mean and individual ADA titer will be presented graphically by cohort over time.

Relative time to dose includes: baseline; 1 week post IV dose, pre SC dose 1; pre SC dose 2; pre SC dose 3, 1 week post SC dose 3, 3 week post SC dose 3, 5 week post SC dose 3, and 8 week post SC dose 3.

All immunogenicity results will be presented in a data listing.

12. Exploratory Analysis

Blood for PTH will be performed at Screening, and on Day 36 (1 week post SC dose 3) for first participant within each cohort, and on Day 29 (1 week post SC dose 3) for subsequent participants within each cohort.

Bone biomarkers (sCTX, P1NP, osteocalcin) will be performed at below timepoint:

First participant within each cohort	Subsequent participants within each cohort
Day 1 (pre IV dose)	Day 1 (pre IV dose)
Day 36 (1 week post SC dose 3)	Day 29 (1 week post SC dose 3)
Day 65 (5 weeks post SC dose 3)	Day 57 (5 weeks post SC dose 3)

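### The SAP classifies ADA and NAb negatives without using the drug concentration that the protocol pairs with each antibody sample, so a negative that circulating drug may have masked counts as a true negative

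*Protocol*

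**What the plan says.** Protocol Section 3 (Table 4) makes "Incidence of ADAs and NAbs" a secondary endpoint. Protocol Section 8.9 gives a reason for measuring drug alongside antibodies: samples from the same time points "will be evaluated for ALXN1850 concentration to enable interpretation of the antibody data".

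SAP Section 11 then classifies participants from the assay readout alone.

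- Negative: "ADA negative: ADA negative response in the ADA assay at all time points".
- Positive: the class is to "include participant with a positive response in the ADA assay at any time point", subdivided by baseline status and a 4-fold titer rule.
- NAb positive requires a positive NAb result in a participant with a treatment-emergent or treatment-boosted ADA response. Everyone else falls into a residual class: "Or will be NAb negative".
- Both are reported by cohort: each "will be summarized as absolute occurrence (n) and percentage (%) by cohort".

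SAP Section 4.4 admits to the Immunogenicity Analysis Set any treated participant "who after the first dose have at least one reportable result in the ADA assay". It does not define a reportable result or link it to drug level.

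Drug level and ADA appear together in two places. In SAP Section 8.2, "mean plasma concentrations of ALXN1850 versus nominal time will be plotted for each treatment by ADA status". SAP Section 8.3 overlays PK parameters and ADA titers for each participant.

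**The concern.** Circulating drug can bind antibody and hide it from the assay. A negative drawn above the assay's drug tolerance therefore does not show that antibody is absent, which is the usual reason to measure drug in parallel. The protocol states that purpose, but the SAP has no tolerance limit, no inconclusive category and no rule that uses the matched concentration. As written, a participant whose only post-dose samples were drawn with drug on board, all negative, counts as ADA negative and, by default, NAb negative.

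The status also feeds other outputs. It splits the concentration plots (SAP 8.2), the dose-proportionality and bioavailability analyses (8.4), the adverse event tables (9.1) and the PD summaries (10). The plots by ADA status cannot reveal a masked negative, because they take the classification as given: a participant whose antibody was hidden by high drug would sit in the negative group. Any masking would depend on dose, so it would distort the comparison across cohorts as well as the level within one.

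**Working it through.** The plan states no figure to reproduce: the sample size is empiric and no hypotheses are planned. Four checks follow.

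**1. Do the data for a drug-level rule exist?** Compare the ADA days (SAP 11) with the PK days (SAP 8.2).

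- First participant: ADA on Days 1, 8, 15, 22, 29, 36, 51, 65, 85. All 9 are PK days.
- Subsequent participants: ADA on Days 1, 8, 15, 22, 29, 43, 57, 78. All 8 are PK days.

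Every antibody sample has a concentration to match. In subsequent participants, 4 of the 7 post-dose samples (Days 8, 15, 22, 29) fall 168 h after a dose. The other 3 (Days 43, 57, 78) fall 21, 35 and 56 days after the last dose on Day 22.

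**2. How does the risk scale with dose?** Protocol Table 5 predicts, for SC dosing, AUC 441 at 15 mg and 2645 at 90 mg, and Cmax 3.2 and 19 µg/mL. The ratios are 2645/441 = 6.0 and 19/3.2 = 5.9. For any fixed tolerance limit that both cohorts start above, the 90 mg cohort stays above it for log2(6) = 2.6 half-lives longer.

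**3. How much drug is left at each visit?** The half-life is an assumption. A remark in the protocol's amendment history puts the end-of-treatment visit at 5.5 half-lives. Day 22 to Day 57 is 35 days, so the half-life is 35/5.5 = 6.4 days. I also ran 4 and 10.2 days. The approximation is

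residual = predicted SC Cmax × 0.5^(days since last dose / half-life).

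For Day 29 at 90 mg this is 19 × 0.5^(7/6.4) = about 8.9 µg/mL.

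| Day (days since dose) | 15 mg, µg/mL (range for 4 to 10.2 d) | 90 mg, µg/mL (range for 4 to 10.2 d) |
|---|---|---|
| 29 (7) | 1.5 (0.95 to 2.0) | 8.9 (5.6 to 11.8) |
| 43 (21) | 0.32 (0.08 to 0.77) | 1.9 (0.50 to 4.6) |
| 57 (35) | 0.07 (0.007 to 0.30) | 0.42 (0.04 to 1.8) |
| 78 (56) | 0.007 (0.0002 to 0.07) | 0.04 (0.001 to 0.42) |

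The extra time above a fixed limit at 90 mg is 2.6 × 6.4 = about 16 days (10 to 26 days over the range).

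These are orders of magnitude. The method ignores absorption and adds no accumulation. Table 5 is not exactly dose-linear either: IV AUC per mg is 325/15 = 21.7, 1084/45 = 24.1 and 1951/90 = 21.7. A one-compartment reading of the 15 mg IV row (Cmax 4.3, AUC 325) gives a half-life of only about 2.6 days, at which Day 29 at 90 mg would be 19 × 0.5^(7/2.6) = 2.9 µg/mL. A shorter half-life makes the late samples cleaner.

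**4. What does one misclassified participant do?** With 5 in a cohort, 1/5 = 20 percentage points. With 3, 1/3 = 33 points.

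**The case against.** The strongest reply is that the design already guards against masking. Classification is by participant, one positive at any visit suffices, and three visits fall in washout. On the approximation above, a participant with lasting ADA who attends every visit is missed at 90 mg only if the tolerance is below about 0.04 µg/mL (0.001 to 0.42 over the assumed half-lives). This stands. It removes most of the risk to the headline ADA incidence in those who attend the late visits.

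Second, the assay is to be validated, and its tolerance may exceed every level in the table, in which case nothing changes. This stands too, and neither document settles it. A reader might infer that ADA incidence will be biased downwards, most at 90 mg. The documents support only that it can be.

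Third, a reader might take the plan to enrol about 15 so that at least 9 complete as meaning that up to 6 could leave early with on-drug samples only. It does not mean that. Completion requires all doses and all PK/PD samples within window (Protocol 9.2), and a participant who misses a dosing visit may stay on through the end-of-treatment assessments (Protocol 7.2). The protocol also asks for a final-visit serum sample from those who discontinue (8.9), encourages the remaining scheduled evaluations (7) and replaces some participants (7.2). The documents give no number of early leavers. For someone who leaves soon after a dose, though, the final sample may itself be on-drug.

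Fourth, concentrations and antibody results are both listed, so with about 5 per cohort a reader could pair them by hand. That is true, but it leaves the reported incidence and every table split by ADA status unchanged.

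Fifth, a reader might expect time of ADA onset to be distorted. SAP 11 plans no onset analysis, so no such output is at risk. The by-visit titer summaries are planned and are exposed. Finally, since a reportable result is undefined, the laboratory might already withhold on-drug negatives. If so, the SAP should say it.

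**Conclusion.** The gap is real: the protocol's stated use of the paired concentration does not reach the SAP's ADA and NAb classification. Its consequence is conditional on the assay's drug tolerance, which is not in the documents, and if masking occurs it acts towards fewer positives, more so at 90 mg.

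The exposure is limited to participants without washout samples, transient responses, NAb status and by-visit titer summaries, together with the PK, PD and adverse event outputs that inherit ADA status. Where it applies, one participant is worth 20 points in a cohort of about 5. This is a cheap improvement and not a flaw that undermines the secondary endpoint. The 6-fold contrast is a prediction from Table 5, and the residual levels rest on an assumed half-life.

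**What to change.** In SAP Section 11:

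1. State the validated drug tolerance of the ADA assay and of the NAb assay.
2. Flag a negative sample as inconclusive when its matched ALXN1850 concentration is above the relevant tolerance, and show the flag in the listing and the by-visit titer summaries.
3. Call a participant ADA negative only with no positive and at least one conclusive post-dose negative; otherwise call the participant not evaluable. Apply the same logic to NAb in place of the residual class.
4. Report incidence both ways: under the current definition and over evaluable participants.

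In SAP Section 4.4, define a reportable result.

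The cost is SAP wording and a merge of ADA and PK data already collected on the same days, with no new sampling. The downside is that a few participants may move from negative to not evaluable. If the tolerance exceeds all observed concentrations, no result changes and the report can show that its negatives are sound.
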